# 8 Efficacy Analysis

All efficacy analyses pertaining to the treatment period and extension period will be performed on the FAS Sample, and patients will be included in the treatment group as randomized.

Statistical comparisons are based on 2-sided, 0.05 significance levels.

## 8.1 Primary Efficacy Endpoint

The primary efficacy endpoint is the change from the baseline defined in Section 7.1 to Week 6 in MADRS total score.

[figure not shown]
# 8.1.1 Primary Efficacy Analysis

The null hypothesis of the statistical test comparing CT-152+ADT and sham+ADT, based on the primary efficacy endpoint, is that the change in MADRS total score using CT-152+ADT is equal to the change in MADRS using the sham+ADT.

 $H_0$ :  $\Delta \mu_{MADRS\ CT-152+ADT} = \Delta \mu_{MADRS\ sham+ADT}$ 

Ha:  $\Delta \mu$  madrs ct-152+adt  $\neq \Delta \mu$  madrs sham+adt

The primary analysis will be conducted on the change from baseline in MADRS total score to the final on-therapy evaluation (Week 6) based on the FAS Sample adjusted for the baseline MADRS total score.

for efficacy, or if the p-value of the statistical comparison based on the primary efficacy endpoint at final is < 0.049.

# 8.1.1.1 Primary Estimand

The primary estimand defining the treatment effect of interest in the protocol uses the hypothetical strategy specified in the International Council for Harmonisation (ICH) E9 Addendum. The objective of the primary analysis is to compare the efficacy of CT-152 and sham. The estimand, or target of estimation, following the hypothetical strategy is the treatment effect seen, had no withdrawals occurred. Subjects who withdraw from a CT-152 or sham either could have lost their treatment effect, had the subjects not taken any other treatment after withdrawal, or could have their treatment effect been masked, had the subjects taken other treatment after withdrawal. This means that any observations taken after subjects stop CT-152 or sham will most likely not contribute relevant information about the treatment effect. Due to this strategy, the last collected efficacy assessment after premature trial discontinuation will be done only once at the early termination (ET) visit. Every effort will be made to complete all of the ET evaluations prior to administering any other treatment. In the case of terminal or lost to follow-up events no ET evaluations would be expected, and only scheduled assessments performed before such an event has occurred.

The primary estimand for this trial is defined by the following components:

- Target population: FAS Sample
- Endpoint: change from baseline to Week 6 in the MADRS total score
- Intercurrent events: premature treatment discontinuation
- Measure of intervention effect: difference in endpoint means between CT-152+ADT and sham+ADT

In this hypothetical strategy, the event of withdrawing CT-152+ADT or sham+ADT is considered missing at random (MAR), and the primary endpoint of the trial could be considered as a combination of the measurements of on-treatment completers at Week 6 and the imputation of the endpoint to Week 6 following the trend in each treatment group using the mixed model repeated measurements (MMRM) method to impute missing data for subjects who withdraw CT-152+ADT or sham+ADT during the trial. All data collected during the trial treatment period will be used for statistical analysis. For the primary efficacy analysis, the treatment effect will be estimated using the MMRM method described below.

Under the MAR assumption, MMRM provides an unbiased estimate of treatment effect for the treatment period. Analyses with missing values imputed by multiple imputation under missing not at random (MNAR), and other methods will be performed as sensitivity analyses.

## 8.1.1.2 Primary Analysis Method

The primary analysis will utilize a MMRM with an unstructured (UN) variance covariance matrix in which the change from baseline in MADRS total score at scheduled treatment period visits (Weeks 2, 4, and 6) will be the dependent variable based on the OC data set on FAS Sample. The model will include fixed class effect terms for treatment, visit, treatment by visit interaction, and site to assess heterogeneity of treatment effects. This model will also include an interaction term of visit by baseline MADRS total score as a covariate. The primary comparison between the CT-152+ADT or sham+ADT at Week 6 will be estimated as the difference between least squares means utilizing the computing software SAS procedure PROC MIXED.

The mathematical formula for the MMRM model is as follows:

$$\mathbf{y} = \mathbf{X}\boldsymbol{\beta} + Z\mathbf{u} + \epsilon$$

Where

y denotes the observed vector of change from baseline to Week 6 in MADRS total score;

X is the known matrix for the fixed effects and covariate;

 $\beta$  is an unknown fixed-effect parameter vector;

Z is the known matrix for the random effect of subject;

u is an unknown vector of random effect of subject with mean  $\mathbf{0}$  and variance-covariance matrix  $\mathbf{G}$  (unstructured covariance matrix);

 $\epsilon$  is an unknown vector of random errors with mean 0 and variance **R**.

In case there is a convergence problem with the MMRM model with the unstructured variance-covariance matrix, the following structures other than unstructured will be used in order of 1) heterogeneous toeplitz (TOEPH), 2) heterogeneous autoregressive of order 1 (ARH1), and 3) heterogeneous compound symmetry (CSH). The first (co)variance structure converging to the best fit will be used as the primary analysis. If a structured covariance has to be used, the "sandwich" estimator of the standard error of the fixed effects parameters will be used in order to deal with possible model misspecification of the covariance matrix.

Small trial sites will be defined as trial sites that do not have at least one evaluable subject (evaluable with regard to the primary efficacy variable) in each treatment arm. All small trial sites will be pooled to form "pseudo sites"

#### 8.1.2 Technical Computation Details for Primary Efficacy Analysis

The SAS code for the PROC MIXED procedure to carry out the above MMRM analysis with an unstructured variance covariance structure is illustrated as follows:

```
proc mixed;
class treatment site visit subjid;
model change=treatment center visit treatment*visit baseline*visit /s cl
ddfm=kenwardroger;
repeated visit /type=un subject=subjid r rcorr;
lsmeans treatment*visit / pdiff cl alpha=0.05 slice=visit;
run;
```

where baseline is the last available measurement prior to the start of intervention with doubleblind digital therapeutic in the treatment period.

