#### 8.1.4 Subgroup Analyses

Subgroup analyses of change from baseline in MADRS total score to every scheduled visit in the treatment period will be performed by the following factors:

- Sex (Based on the biological status)
- Race (White and All Other Races)
- Age group (Age < 55 and Age  $\ge 55$ )
- Cannabis use (subjects reporting current cannabis use at screening or with positive THC test results at screening)

All subgroup analyses will be conducted using the same MMRM analysis as for the primary efficacy analysis except that the fixed class effect term for trial center will not be included in the model.

Interaction effects of treatment-by-subgroup will be assessed at Week 6 for the subgroups identified in the previous paragraph. MMRM analyses will be performed by adding addition of terms for subgroup-by week and treatment-by-subgroup-by-week. These treatment-by-subgroup interaction analyses will be presented in statistical documentation.

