### 3.1 Planned Interim Analyses of Unblinded Efficacy data

A set of pre-specified tables (see Appendix 1) will be produced at the planned interim analysis following statistical methods described in the Trial 345-201-00002 SAP. The Otsuka Pharmaceutical Development & Commercialization, Inc. (OPDC) Biometrics will provide blinded SAS datasets and SAS programming codes to the IDAG statistician. The OPDC Biometrics will also provide authorization for the IDAG statistician to get the randomization directly from IVRS or IWRS vendor. The IDAG will produce all prespecified summary tables using the SAS codes and analysis datasets provided by OPDC Biometrics.

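### The illustrative SAS code for the primary MMRM declares `site` in CLASS but uses `center` in MODEL, so it does not fit the site class effect that the SAP text specifies

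*SAP*

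**What the plan says.** The specification is in SAP 8.1.1.2: "The model will include fixed class effect terms for treatment, visit, treatment by visit interaction, and site to assess heterogeneity of treatment effects". Protocol 9.4.1.1.2 also lists site as a fixed effect, and Interim Analysis Plan 2.2 repeats the class-effect wording. Randomization is stratified by trial site across about 50 sites (SAP 3), and small sites are pooled for analysis (SAP 8.1.1.2 and 10.2).

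SAP 8.1.2 then gives the only code for this analysis, introduced with "The SAS code for the PROC MIXED procedure to carry out the above MMRM analysis with an unstructured variance covariance structure is illustrated as follows". Its CLASS statement reads "class treatment site visit subjid" and its MODEL statement begins "model change=treatment center visit treatment*visit baseline*visit /s cl".

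Elsewhere the SAP uses site and center for the same factor. SAP 8.1.4, for example, says of the subgroup models that "the fixed class effect term for trial center will not be included in the model". The SAP addendum of 16 Nov 2022 leaves the statistical methods unchanged unless it says otherwise, and its sections do not touch this code.

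For the interim analysis, Interim Analysis Plan 3.1 states: "The IDAG will produce all prespecified summary tables using the SAS codes and analysis datasets provided by OPDC Biometrics".

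**The concern.** PROC MIXED treats any MODEL variable that is missing from CLASS as continuous. The code as printed therefore cannot produce the specified model. The outcome that matters is the one that runs: a numeric center code would receive a single slope on an arbitrary number, and the log would show no error.

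Site is the stratification factor. If its class effect is lost, between-site variance stays in the residual, and the model standard error no longer reflects the balance that stratification achieved. The primary p-value of a pivotal trial would then come from a model other than the prespecified one. If a programmer corrects the slip silently, the program departs from the signed SAP code. If nobody corrects it, the analysis departs from the SAP text.

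**Working it through.** **1. The plan's own figure.** The inputs are a difference of 3 points, SD 9, two-sided alpha 0.05 and power 85% (SAP 4). Per arm, n = 2 × (1.960 + 1.036)² × 9² / 3² = 161.6, rounded up to 162, so 324 evaluable. Allowing for 10% non-evaluable, 324 / 0.90 = 360. Both figures reproduce. Power with 162 per arm is 85.1% by the normal approximation (84.9% by the t-test), and 84.9% at the final alpha of 0.049 (normal approximation). The code mismatch changes none of these.

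**2. Text against code.**

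| Source | How site enters | Degrees of freedom |
|---|---|---|
| SAP 8.1.1.2 text | fixed class effect | number of pooled sites − 1, up to about 49 |
| SAP 8.1.2 code, numeric `center` | one linear slope | 1 |
| SAP 8.1.2 code, character or absent `center` | step stops | none |

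The silent linear fit needs a dataset that holds a variable `site` (otherwise CLASS fails) and also a numeric `center` (otherwise MODEL fails). The documents describe no such dataset. Protocol 5.1 gives the site number as 3 digits but does not say how it is stored.

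**3. Size of the effect if the linear fit were run.** Two simulations compare a linear site code with class site at Week 6. Both use 50 sites, about 324 subjects, total SD 9, a true difference of 3 points and alpha 0.049. Simulation A uses permuted blocks of 2 and 4 within site and 2,500 runs. Simulation B uses blocks of 4 and 1,500 runs per cell. The site ICC and the block sizes are assumptions, because the documents give neither.

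| Site ICC | Simulation | Power, linear | Power, class | Linear − class (points) | Type I error, linear | Type I error, class |
|---|---|---|---|---|---|---|
| 0 | B | 84.9% | 84.1% | +0.8 | 5.0% | 5.3% |
| 0.02 | B | 86.0% | 85.8% | +0.2 | 4.1% | 4.4% |
| 0.05 | A | 86.4% | 86.6% | −0.2 | 4.4% | not available |
| 0.05 | B | 85.7% | 85.5% | +0.2 | 3.9% | 5.3% |
| 0.10 | A | 85.8% | 87.6% | −1.8 | 4.2% | not available |
| 0.10 | B | 87.1% | 88.3% | −1.2 | 4.3% | 4.7% |
| 0.15 | A | 86.5% | 89.5% | −3.0 | 3.6% | not available |
| 0.20 | B | 86.0% | 90.8% | −4.8 | 3.2% | 5.7% |

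Monte Carlo standard errors for type I error are √(0.049 × 0.951 / 2,500) = 0.43 points in A and √(0.049 × 0.951 / 1,500) = 0.56 points in B. For power in B the figure is about √(0.85 × 0.15 / 1,500) = 0.9 points.

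**4. Why the test is conservative.** In simulation B at ICC 0.20, the estimates from the two models vary almost equally from run to run (SD 0.92 for each), and both average −2.99 for a true −3. The mean model standard error is 0.986 with the linear code and 0.903 with class site, a ratio of 0.986 / 0.903 = 1.09. The linear fit overstates the uncertainty and does not shift the estimate. In simulation A the standard error is larger by 1.6%, 4.2% and 6.8% at ICC 0.05, 0.10 and 0.15.

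**The case against.** The strongest reply is that this is a naming slip in an example. The code is offered as an illustration, names no dataset, and follows text that leaves no doubt about the model. Because the SAP uses site and center interchangeably, a statistician reading 8.1.1.2, 8.1.2 and 8.1.4 together would fit a class effect. The `/s` option prints the fixed-effect solution, so a single slope for center in place of a row per site would be visible to anyone who looked. All of this stands, and it limits the severity. It does not make the printed code correct.

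The simulated losses also deserve discount. They come from a one-visit linear model, not the three-visit MMRM with Kenward-Roger degrees of freedom. The MADRS is rated by telephone by raters managed centrally, apart from the sites (Protocol 4.1 and 8.1.1). That removes the site rater as a source of between-site variance and makes an ICC of 0.15 to 0.20 less plausible.

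A reader might infer that the interim p-value, the 0.003 decision and the conditional-power zones are affected. The documents do not support that. Interim Analysis Plan 3.1 says that the independent group runs sponsor-supplied programs following the SAP methods. It does not say that those programs contain this snippet. The Interim Analysis Plan (13 Oct 2021) is dated before SAP version 1.0 (11 Feb 2022), and its methods section states the class-effect model in words, without code. The production programs cannot be seen.

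**Conclusion.** The mismatch is real, and the addendum sections do not correct it. As printed, the code does not fit the model specified in SAP 8.1.1.2. It is a minor, correctable inconsistency.

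If `center` were numeric and the code were run literally, the treatment difference would remain unbiased and the test would become mildly conservative. The power cost would be about 0 to 2 points for a site ICC of 0 to 0.10 and about 3 to 5 points for 0.15 to 0.20, all on assumed ICC values. Simulated power under the linear fit lies between 84.9% and 87.1%. That is no shortfall against the stated 85% within simulation error: the sample size calculation states no allowance for site adjustment, so what is lost is a gain on which the plan did not count.

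Three stronger readings should be avoided: that the SAP prescribes a linear site term, that the wrong model was actually run, and that false positives become more likely. The governing text contradicts the first, the documents cannot establish the second, and the simulations show no inflation from the linear fit.

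**What to change.** Use one variable, the pooled site defined by SAP 8.1.1.2 and 10.2, in both statements:

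`class treatment poolsite visit subjid;`

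`model change = treatment poolsite visit treatment*visit baseline*visit`

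The remaining options stay as they are. State in SAP 10.2 that this variable carries the pooled factor, so that site, center, pseudo site and pooled center all refer to one thing. Confirm that the program supplied to the independent data analysis group uses the same variable as a class effect. The cost is one name changed in each of two statements, one clarifying sentence and a program check. The sample size, alpha levels and stated model do not change.

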# 8.1.3 Sensitivity Analyses

## 8.1.3.1 Sensitivity Analyses for Missing at Random (MAR) Assumption

Traditionally the dropout mechanisms are divided into three types (Little, 1995): (1) Missing Completely at Random (MCAR), in which the probability of dropout doesn't depend on the observed data and the missing data; (2) Missing at Random (MAR), in which the probability of dropout depends on the observed data, and (3) Missing Not at Random (MNAR), where the probability of dropout depends on the missing data and possibly the observed data.

Most of MNAR methods (Diggle P, Kenward MG, 1994) have treated all observations with dropout as if they fall within the same dropout type. In practice, we would find that different dropout reasons may be related to the outcomes in different ways, for example, detailed dropout reasons for this study are: adverse events (AE), lack of efficacy (LOE), lost to follow-up, protocol deviation, sponsor discontinued study, subject met (protocol specified) withdrawal criteria, subject was withdrawn from participation by the investigator, and subject withdrew consent to participate. Dropout due to an AE and LOE may lead to MNAR dropout. Subject withdrew consent may also lead to MNAR dropout. However, it is debatable whether

a dropout caused by subjects withdrew consent is MAR or MNAR. Except AE, LOE, and subject withdrew consent, all the other dropout reasons may be assumed as either MCAR or MAR dropout. Dropout due to COVID-19 will also be assumed as MAR.

As sensitivity analyses for missing at random (MAR) assumption, analyses for missing not at random (MNAR) will be carried out. Pattern Mixture Models (PMM) based on Multiple Imputation (MI) with mixed missing data mechanisms will be used to investigate the response profile of dropout patients by last dropout reason under MNAR mechanism for the following three scenarios:

- 1) Dropout reasons due to either AE or LOE as MNAR
- 2) Dropout reasons due to either AE or LOE or subject withdrew consent as MNAR
- 3) All dropouts as MNAR

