4.5 Definition of Completed Subjects

Subjects who are evaluated at their last scheduled visit will be defined as trial completers. For purposes of this trial, subjects who complete the Trial Day 70 assessments will be defined as trial completers.

5 Trial Population

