7.3 Individual Subject Discontinuation

7.3.1 Treatment Interruption

A subject may remain in the trial, even if nonadherent with the treatment sessions during the treatment period; all trial procedures should still be performed, including the primary and secondary endpoints and documentation of AEs and pharmacologic or other treatments that may have occurred.

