# 4 Sample Size and Power Justification

The primary efficacy endpoint is the change from baseline at Week6 in Montgomery-Asberg Depression Rating Scale (MADRS) total Score. The trial will compare CT-152 to sham, randomized at a ratio of 1:1, with an overall alpha of 0.05 for the primary efficacy endpoint.

The initial sample size is calculated to detect a 3-point difference between CT-152+ADT and sham+ADT in the change from baseline in MADRS total score with 85% power at a 2-sided  $\alpha$  = 0.05 level, assuming a common standard deviation of 9. The resulting sample size is 324 evaluable subjects in total (162 subjects in each arm). To compensate for subjects that fail to have evaluable assessments of MADRS total score in the full analysis set (FAS) Sample (estimated at up to 10% of all subjects), a total of 360 subjects (180 subjects in each arm) will be randomized in this trial.

Due to the limitations of applying assumptions on the treatment effect size, and in order to ensure adequate power of the trial, an unblinded interim analysis (IA) will be conducted by a Data Monitoring Committee (DMC) on when approximately the first 180 randomized subjects had an opportunity to complete the Week 6 visit. The final sample size could be increased to 540 subjects (270 subjects in each arm) as per recommendation of the DMC. Using the O'Brien-Fleming spending function, an alpha level of 0.003 (2-sided) is allocated to this interim analysis. The alpha level left for the final analysis is 0.049 (2-sided). The power and sample size were obtained using the PASS 14 (2015) statistical computing software.

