#### **Delta Adjustment Imputation Methods**

This MNAR sensitivity analysis is to departure from MAR assumption by progressively increasing the delta until conclusion from the primary analysis is overturned. The delta is 0%, 10%, 20%, 30%, ..., 100% of the expected treatment difference of 3 points and/or the observed treatment difference between CT-152 and sham from the primary analysis of MMRM model until conclusion of the primary analysis is overturned. When delta=0 it is MAR. When delta > 0 it is MNAR.

- Using Monte Carlo Markov Chain (MCMC) methodology from PROC MI to impute the intermittent missing data to a monotone missing pattern
- 2) Using a standard MAR-based multiple imputation approach from PROC MI to impute the monotone missingness data
- 3) For patients in the treated group and with a dropout reason of AE or LOE or subject withdrew consent, a delta will be added for all the values after the dropout time
- Using analysis of covariance (ANCOVA) model to analyze the completed data through multiple imputation.
- 5) Obtaining the overall results using PROC MIANALYZE.

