#### 10 Conventions

## 10.1 Study Visit Windows

Study visit windows will be used to map visits using study day intervals. Observations at each scheduled visit and Early Termination will be assigned to Week 2, Week 4, Week 6, Week 8 and Week 10 based on their visit windows as shown in Table 10.1-1. This visit window convention applies to tables and listings for all efficacy scales (MADRS, GAD-7, CGI-S, PHQ-9, WHODAS2.0, CCI, and CCI). This derived study window variable will be named as WEEK and will be footnoted. In listings it will be listed along with the eCRF study visit.

Table 10.1-1 shows classifications for study day intervals in the treatment period and extension period. The variable "target day" is defined using the number of days since the start of intervention with double-blind digital therapeutic in the treatment period. The first day of intervention with double-blind digital therapeutic is defined as "Day 1". If more than one observation falls within a particular study day interval, then the last observation within that interval is used. Assessments done during the treatment period and occurring more than seven days after the last date of the interaction with double-blind digital therapeutic in the treatment period will be excluded from efficacy analyses of the treatment period.

[figure not shown]
SAP 345-201-00002

Table 10.1-1 Study Day and Visit Windows in the Trial					
Week	Target Day a	Study Day Interval a			
2	14	2~20			
4	28	21~34			
6	42	35~48			
8	56	49-62			
10	70	63-77			

<sup>a Relative to the first day of intervention with double-blind digital therapeutic in the treatment period.

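### As written, the delta (tipping-point) analyses put no penalty on CT-152 subjects who stop the app, stay in the trial and lose their Week 6 rating to the seven-day rule in SAP 10.1

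*SAP*

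**What the plan says.** - **Staying in without using the app.** Protocol 7.3.1: "A subject may remain in the trial, even if nonadherent with the treatment sessions during the treatment period", with the primary endpoint still collected. Protocol 7.3.4 adds that wanting to stop the app is not the same as withdrawing consent. Under Protocol 4.5, "subjects who complete the Trial Day 70 assessments will be defined as trial completers", so a subject who stopped the app can still be a completer.
- **Which ratings are removed.** SAP 10.1: treatment-period assessments "occurring more than seven days after the last date of the interaction with double-blind digital therapeutic in the treatment period will be excluded" from the treatment-period efficacy analyses.
- **Who is treated as MNAR.** SAP 8.1.3.1 aims to "investigate the response profile of dropout patients by last dropout reason under MNAR mechanism", in three scenarios defined by dropout reason. The widest takes every dropout as MNAR. The listed reasons include withdrawal of consent to take part, withdrawal by the investigator and the sponsor ending the study.
- **Who receives delta.** All monotone missing values are first imputed under MAR. Delta is then added "For patients in the treated group and with a dropout reason of AE or LOE or subject withdrew consent", for values after the dropout time. IAP 2.2.1 has the same steps. It allows the DMC to weigh an efficacy stop on a delta analysis with the full penalty on all CT-152 dropouts.
- **The estimand.** SAP 8.1.1.1 and Protocol 9.4.1.1.1 name one intercurrent event, premature discontinuation of treatment. Both also say that all data from the treatment period will be analysed, and Protocol 9.4.1.1.2 says the same of observed data from the planned visits.

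The November 2022 SAP addendum does not change these rules.

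**The concern.** The plan creates two kinds of missing Week 6 value. One belongs to subjects who leave the trial. The other belongs to subjects who stop the app, stay and are rated, but whose rating SAP 10.1 removes. The delta analyses are keyed to the first kind, while the estimand's intercurrent event covers both.

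A tipping-point analysis is meant to show how much worse the imputed subjects would have to be before the conclusion fails. If some of them never receive delta, the conclusion looks harder to overturn than was tested. The same applies to the interim check that may support stopping for efficacy.

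**Working it through.** **1. The plan's own figure.** Inputs from SAP 4: equal allocation and a two-sided 0.05 level; a target of 3 points at 85% power ("The initial sample size is calculated to detect a 3-point difference between CT-152+ADT"); and the spread ("assuming a common standard deviation of 9").

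n per arm = 2 × (1.960 + 1.036)² × 9² / 3² = 161.6, so 162 per arm and 324 in total; 324 / 0.90 = 360. The stated sizes reproduce. The standard error is 9 × √(2/162) = 1.0.

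**2. When a rating is lost.** A rating on Day 42 is excluded if last use was Day 34 or earlier (42 − 34 = 8 days). For a Day 45 rating the limit is Day 37.

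**3. A CT-152 subject who stopped, stayed and lost the Week 6 rating, followed through the plan** (taking dropout to mean leaving the trial):

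| Analysis | Treatment of this subject | Uses the excluded rating? |
|---|---|---|
| Primary MMRM | own-arm MAR | No |
| Delta, scenarios 1 to 3 | own-arm MAR, delta = 0 | No |
| Interim full-penalty check | own-arm MAR, delta = 0 | No |
| Sham-based imputation | imputed from the sham model | No |
| Shared-parameter and random-coefficient pattern-mixture models | may be reached, depending on how missingness is coded | No |
| LOCF ANCOVA | earlier rating carried forward | No |
| OC ANCOVA | absent at Week 6 | No |
| Randomized Sample multiple imputation | MAR | No |

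The exclusion covers treatment-period efficacy analyses only. Week 8 and 10 ratings are not covered by it, and the MADRS suicidal-thoughts item still feeds SAP 9.3.1.

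**4. Size.** The documents give no rate for stopping but staying, so the shares are assumptions. Shift in the Week 6 difference = delta × share of the CT-152 arm that receives it. With delta = 3 and 10% dropouts, the planned shift is 3 × 0.10 = 0.30. For the p-values, take an observed difference of 2.5 (p = 0.012 before any delta), hold the SE at 1.0 and use z = (2.5 − shift) / 1.0.

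| Stop but stay | Shift if included | Left untested | p at full delta, as planned | p if included |
|---|---|---|---|---|
| 5% | 0.45 | 0.15 | 0.028 | 0.040 |
| 10% | 0.60 | 0.30 | 0.028 | 0.057 |
| 20% | 0.90 | 0.60 | 0.028 | 0.110 |

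Against 0.049, the robustness conclusion changes at 10% and 20% but not at 5%. With an observed difference of 3.0 it does not change even at 20% (p = 0.036).

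**5. Check by simulation.** Settings: 600 trials, 162 per arm, 5 imputations, SD 9, within-subject correlations 0.5 to 0.7, true effect 3 points, 10% dropouts, 10% stopping but staying, and a 3-point loss off the app in CT-152. Mean Week 6 differences:

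- MAR: −2.94
- delta on dropouts only, as planned: −2.64
- delta on both groups: −2.34
- delta on dropouts, with the observed ratings of those who stayed: −2.33
- sham-based imputation: −2.63

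The planned maximum delta stops about 0.30 points short, as in step 4.

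**The case against.** **The exclusion may not apply.** If the statements that all treatment-period data are used prevail over SAP 10.1, no rating is removed and the gap disappears. This stands: the point is conditional, and reconciling those sections comes first.

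**Dropout is undefined.** Protocol 7.3.3 lists similar reasons for stopping the app, and SAP 8.1.1.1 speaks of withdrawing the treatment, so dropout could be read at treatment level. That is possible but not stated. The reasons in SAP 8.1.3.1 point to leaving the trial, and the term needs defining either way.

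**The group may be small.** The seven days run from the last interaction, also undefined. If reading the adherence code at the Week 5 contact (about Day 35) counts, a Day 42 rating is exactly seven days later and is kept. Subjects who discontinue before Week 6 are also due an early termination visit soon after last use. Both arguments limit the size; neither removes the gap.

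**Total loss of effect is the extreme case.** Someone stopping on Day 34 could have done about 15 of 18 sessions. With half the effect retained, the loss missed would be half the step 4 figures: about 0.08, 0.15 or 0.30 points. This stands as a limit on the likely loss, although the plan's own delta range runs to the full 3 points.

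**Other MNAR analyses exist.** A reader might infer that no MNAR analysis reaches these subjects. The documents do not support that: sham-based imputation covers all missing data, and the two model-based methods may reach them. None of these repairs the tipping point or uses the excluded ratings.

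**Conclusion.** The point holds for the delta analyses in SAP 8.1.3.1 and IAP 2.2.1, on two conditions: SAP 10.1 governs, and dropout means leaving the trial, as the listed reasons suggest. Part of the imputed CT-152 group then stays at MAR under every delta, and no planned treatment-period efficacy analysis shows the ratings that were collected. Under assumed shares of 5% to 20%, the untested part is 0.15 to 0.60 points. That can matter for a result near 2.5 points and need not for one near 3.

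Three stronger readings should be resisted:

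- **That the primary analysis is wrong.** Own-arm MAR imputation is consistent with the hypothetical estimand, which itself regards observations after stopping as largely uninformative. The weakness is an untested assumption in a sensitivity analysis.
- **That the trial is underpowered for its target.** If 15% or 25% stopped with no retained effect, the as-randomized difference would be 2.55 or 2.25 points. Power at 0.049 would be about 72% or 61%. The plan does not target that difference.
- **That staying in without using the app is the usual way subjects stop.** The documents give no figures on this.

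The sponsor should correct this, because the tipping point may inform both the final interpretation and the DMC's efficacy recommendation.

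**What to change.** 1. Reconcile SAP 10.1 with SAP 8.1.1.1 and Protocol 9.4.1.1 (9.4.1.1.1 and 9.4.1.1.2), stating whether treatment-period ratings made more than seven days after last app use enter the efficacy analyses, and what counts as an interaction.
2. If the exclusion stays, define dropout in SAP 8.1.3.1 and IAP 2.2.1 to include stopping the app while remaining in the trial. Make scenario 3 and its delta step cover every CT-152 subject whose Week 6 value is missing, or was excluded after stopping the app. Do not count subjects who completed the sessions and were merely rated late in the window: last use on Day 39 and a rating on Day 47 would trip the seven-day rule without any early stop. In the same edit, align the delta step with the scenarios, since it names three reasons while scenario 3 covers all dropouts.
3. Run the MMRM once more, labelled supplementary because it addresses a different estimand, with all collected Week 2 to 6 MADRS ratings kept regardless of last app use.

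**Cost:** wording in the SAP and IAP, one flag in the analysis dataset and one extra model run. No new data are needed. The tipping point may look slightly less favourable.
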